2 STUDY OBJECTIVES AND PURPOSE

2.1 **Primary Objective(s)**

The primary objective of this trial is to evaluate efficacy of JBT-101 for treatment of inflammatory pain related to active musculoskeletal disease in SLE.

For evaluation of this objective, the primary efficacy analysis will compare longitudinal changes in daily measures of the maximum pain NRS in treated groups compared to the placebo group after 12 weeks of treatment.

2.2 Secondary Objective(s)

The secondary objectives are to:

- 1. Evaluate efficacy of JBT-101 in active musculoskeletal disease in SLE
- 2. Evaluate efficacy of JBT-101 in overall disease activity in SLE
- 3. Evaluate efficacy of JBT-101 in patient-reported outcomes in SLE
- 4. Evaluate the safety and tolerability of JBT-101 in subjects with SLE
- 5. Evaluate the effects of JBT-101 on biomarkers of inflammation in SLE
- 6. Evaluate the effects of JBT-101 on bioactive lipids in SLE
- 7. Evaluate JBT-101 plasma concentrations and metabolites in SLE

2.3 Exploratory Objectives

The exploratory objectives of this trial are:

- 1. Explore impact of JBT-101 on symptoms of fibromyalgia
- 2. Explore relationships between JBT-101 plasma concentrations and efficacy, SAEs, biomarkers of inflammation, and certain SPMs, including lipoxin A4

3 STUDY DESIGN

3.1 Description of Study Design

This study is a randomized, double-blind, placebo-controlled, multi-center clinical trial to test the efficacy, safety, and tolerability of JBT-101 compared to placebo for the treatment of SLE, to evaluate JBT-101's impact on SPMs and biomarkers of inflammation in SLE, and to determine JBT-101 plasma concentrations and metabolites in SLE subjects. The target population is SLE subjects ≥ 18 and ≤ 70 years of age with active musculoskeletal disease (arthritis and/or tendonitis) and 7-day average of maximal daily pain NRS score ≥ 4 of 10 (at least moderate pain) at Screening. If applicable, subjects must be on stable doses of corticosteroids ≤ 10 mg daily prednisone or equivalent prior to assessment of screening daily pain NRS score and non-increasing doses of other immunosuppressive medications for at least 3 months. Additionally, subjects must be on a stable dose of any anti-malarial drug for at least 3 months prior to screening or have a history of intolerance, contraindication, or unwillingness to take an anti-malarial drug.

One hundred eligible subjects will be randomized in a 1:1:1:1 ratio to one of four cohorts to receive assigned study treatment (see Table 1 below). On Days 1-84, study product (JBT-101 or matching placebo) will be self-administered orally b.i.d., with at least 8 hours between doses and without regard to fed state. Randomized eligible subjects will take the 1st dose of study medication in the clinic at Visit 1 (Day 1) (See Section 5.3, *Administration of Study Product*).

Cohort	Approximate	Days 1-84	
	n	A.M. Study Product	P.M. Study Product
1	25	JBT-101 5 mg	JBT-101 5 mg
2	25	JBT-101 20 mg	Placebo
3	25	JBT-101 20 mg	JBT-101 20 mg
4	25	Placebo	Placebo

Table 1. Randomization Cohorts

Written informed consent must be obtained prior to the subject undergoing any study-related procedure, including screening tests and washout periods for prohibited medications, when applicable. During the screening period, subjects will be evaluated by the site investigator or qualified designee to assess eligibility for randomization into the study. Screening will take place over multiple days. The subject must report maximum daily pain NRS scores for seven days following the initial visit in the clinic, to ascertain whether eligibility criteria are met with a 7-day average of maximum daily pain NRS score ≥ 4 of 10.

Subjects will report maximum daily pain NRS scores using an interactive voice-response ediary system (IVRS), which can be accessed by any phone that supports tone dialing. At the Screening visit, subjects will be registered and provided with credentials allowing access to the IVRS. Subjects will be instructed on how to record maximum daily pain NRS score, including directions for recording scores at about the same time every day, preferably before bedtime. Subjects who are found to be eligible after the screening evaluation will return for Visit 1 (Day 1) within 42 days of the initial screening visit. Subject eligibility will be confirmed prior to randomization. Randomized subjects will be instructed to continue to record their maximum daily pain NRS score through Visit 6 (Day 113).

There will be six additional study visits; Visits 1-6 on Days 1, 15 ± 3 , 29 ± 3 , 57 ± 3 , 85 ± 3 and 113 ± 3 , respectively. Treatment occurs from Visits 1-5 (Days 1-85), and Visit 6 (Day 113) is a follow-up visit 28 ± 3 days after treatment ends. The 3 day window at Visits is included in case of holidays or unusual circumstances, and it is expected that most if not all visits will be on the targeted day. Vital signs, AEs, prior/concomitant medications, and blood for laboratory safety tests will be evaluated at Visits 1-6 (Days 1-113). On Visit 1 (Day 1), Visit 3 (Day 29), Visit 4 (Day 57), Visit 5 (Day 85) and Visit 6 (Day 113), subjects will also have a physical exam, urinalysis, and other assessments for evaluation of disease status including patient reported outcomes. Psychoactivity of JBT-101 will be assessed using the ARCI-M questionnaire at Visit 1 (Day 1), Visit 3 (Day 29) and Visit 5 (Day 85). Twelvelead ECGs and QT/QTc intervals will be assessed at Screening and at Visit 1 (Day 1) and Visit 5 (Day 85). At Visit 1 (Day 1), the ARCI-M questionnaire and OT/OTc intervals will be assessed both before and 2.5 to 3.5 hours after the first dose of JBT-101, when plasma concentrations of JBT-101 should be about maximal. Study personnel will record the subject's interval medical history, assess AEs and medication use, and collect samples for safety, pharmacokinetic, and mechanistic assessments (see Flow Diagram of Protocol and Section 6, Assessments of Safety and Efficacy; Table 3, Schedule of Events for the specific assessment schedule). Subjects will return study drug bottles for a pill count, and new bottles will be dispensed, as appropriate.

For therapeutic stability, subjects should remain on their current treatment regimen for SLE from Screening through Visit 6 (Day 113), unless the site investigator or other treating physician judges that a change in therapy is needed to provide best medical care for the subject. If a subject experiences an increase in disease activity of SLE during participation in the study, he/she should be treated with standard of care for that increase in activity. If medically appropriate, some drugs that would interfere with evaluation of efficacy should be withheld for specified durations prior to certain study visits. See Section 5.6, *Prohibited Medications* for details.

Concomitant therapies taken for the long term treatment of pre-existing conditions other than SLE may be continued during the study provided they are in accordance with the exclusion criteria (Section 4.2, *Exclusion Criteria*). It is preferred that these medications be stabilized before entry and continued wherever practical without variation of dose or regimen during the study. Concomitant medications and new medications should be administered at the discretion of the site investigator or treating physician in order to provide the subject with the best possible medical care. Because of the unavailability of toxicology data or clinical experience of JBT-101 in combination with many therapeutic agents, it is recommended that changes in ongoing treatments or introduction of new therapies are kept to a minimum. The benefit: risk to the subject should be carefully assessed and consideration given to the timing of any necessary introductions of new medications.

Because this is an early study and no efficacy has been demonstrated in SLE, there are no plans to provide the subject with open-label JBT-101 after the study period. If they so choose, subjects may continue to be seen in the site investigator's clinical practice.

About 150 individuals will be screened to identify 100 eligible subjects, for a screen failure rate of about 33%. The number of subjects enrolled may be expanded by up to nine additional subjects, if these additional eligible subjects have signed the Informed Consent Form and are actively engaged in the screening process at the time 100 subjects have been randomized into the study.

About 15 sites in the United States will participate in this trial. The target enrollment of 100 eligible subjects will take place over about 24 months, for a recruitment rate of about 0.28 subjects per site per month. The feasibility of this plan is judged acceptable, based on expert input from the Protocol Chairs and their collaborators.

The planned total duration of an individual subject's participation in the study is about 112 Days (84 days treatment and 28 days follow-up), plus Screening, unless the subject withdraws prematurely. (See Section 5.8, *Treatment Discontinuation and Subject Withdrawal*.) Once 80% of planned sites are activated, the entire study is expected to take 24-30 months to complete.

3.1.1 Stratification, Randomization, and Blinding

Eligible subjects will be randomized in a 1:1:1:1 ratio to one of four cohorts: 5 mg JBT-101 b.i.d., 20 mg JBT-101 q.d., 20 mg JBT-101 b.i.d., or placebo (see Section 3.1, *Description of Study Design*, Table 1). Subjects will be stratified by 7-day average of maximum daily pain NRS score ≤ 6 versus > 6 and Fibromyalgia Symptom Scale Score < 13 versus ≥ 13 at Screening.

To maintain the study blind, JBT-101 and placebo capsules and their packaging will be identical. All subjects will receive b.i.d dosing to maintain blinding to treatment assignment. In general, clinical staff, including the investigators, will be blinded to the treatment assignments until completion of the study. In addition, they will not have access to any mechanistic data, and mechanistic laboratory staff will not have access to any clinical results until completion of the study. The success of blinding will be formally tested using a Treatment Satisfaction Survey that asks each study subject and corresponding site investigator to guess the study group assignment for that subject at the end of active treatment and then comparing these responses to what would be expected by chance.

Unblinding must be approved by the study Medical Monitor unless an immediate life threatening condition has developed and the Medical Monitor is not accessible. The site investigator will notify the protocol chair(s) and the DAIT- Statistical and Clinical Coordinating Center (SACCC) of the unblinding event on the next business day. The emergency unblinding will also be reported to the Data and Safety Monitoring Board (DSMB).

A full account of the event will be recorded, including the date and time of the unblinding, the reason for the decision to unblind, and the name of the individual who made the decision and the names of the Medical Monitor and others who were notified. The reasons for unblinding of a participant's treatment will be included in the final study report.

An individual's treatment assignment will be unblinded if the subject experiences a suspected adverse reaction that is serious and unexpected (see Section 7.2.1, *Adverse Event* and Section 7.2.1.1 *Suspected Adverse Reaction* and Section 7.2.2, *Unexpected Adverse Event*) or other protocol-specific event(s) determined by DAIT/NIAID to warrant unblinding.

3.1.1.1 Subject Completion and Replacement

A subject is considered to have completed the study if he/she has completed Visit 6 (Day 113).

Randomized subjects who never initiate treatment may be withdrawn and will not count towards the accrual of 100 eligible subjects.

3.2 Description of Endpoints

See Section 6, *Assessment of Safety and Efficacy*, for detailed descriptions of endpoint measures, and Section 8, *Statistical Considerations and Analytical Plan*, for planned analyses.

3.2.1 **Primary Efficacy Endpoint**

The primary endpoint for evaluation of the primary objective will be improvement in maximum daily pain NRS scores in the treated groups relative to the control after 12 weeks of treatment. Longitudinal trends over the course of the treatment period will be modeled and used to estimate differences between means at baseline and Day 84 for each treatment group.

3.2.2 Secondary Efficacy Endpoints

- 1. The 7-day average of maximum daily pain NRS scores prior to Visits 1, 3, 4, 5, and 6 will be used to evaluate the number (%) of subjects with:
 - Changes in pain categories from Visit 1 (Day 1) to Visits 3 (Day 29), 4 (Day 57), 5 (Day 85) and 6 (Day 113) (See Section 6.2.2.2 *Pain Categories*)
 - Improvement of 30% from Visit 1 (Day 1) to Visits 3 (Day 29), 4 (Day 57), 5 (Day 85) and 6 (Day 113)
 - Improvement of 50% from Visit 1 (Day 1) to Visits 3 (Day 29), 4 (Day 57), 5 (Day 85) and 6 (Day 113)
 - Improvement of 75% from Visit 1 (Day 1) to Visits 3 (Day 29), 4 (Day 57), 5 (Day 85) and 6 (Day 113)

- Improvement of 100% from Visit 1 (Day 1) to Visits 3 (Day 29), 4 (Day 57), 5 (Day 85) and 6 (Day 113)
- 2. Trends in active musculoskeletal disease activity over the duration of the treatment period (i.e. Visit 1 (Day 1) through Visit 5 (Day 85)) will be evaluated longitudinally using multiple indices:
 - Physician assessed tender joint count
 - Physician assessed swollen joint count
 - Presence or absence of arthritis on the SELENA SLEDAI
 - Musculoskeletal domain of the BILAG 2004
- 3. Persistence of trends in musculoskeletal disease activity after stopping treatment will be evaluated at Visit 6 (Day 113).
- 4. Trends in overall SLE disease activity over the duration of the treatment period (i.e. Visit 1 (Day 1) through Visit 5 (Day 85)) will be evaluated longitudinally using multiple indices:
 - SLE Responder Index, where a responder is defined as having all of the following:
 - $\circ \geq 4$ point reduction in SELENA-SLEDAI score,
 - no new BILAG A or no more than 1 new BILAG B domain score, and
 - no deterioration from baseline in the Physician's Global Assessment defined as an increase of ≥0.3 points.
 - SELENA SLEDAI score
 - BILAG 2004 score
 - Physician's Global Assessment
- 5. Persistence of trends in overall SLE disease activity after stopping treatment will be evaluated at Visit 6 (Day 113).
- 6. Trends in patient-reported outcomes over the duration of the treatment period (i.e. Visit 1 (Day 1) through Visit 5 (Day 85)) will be evaluated longitudinally using multiple indices:
 - Lupus Activity Patient Global Assessment
 - PROMIS-29 Short Form
 - PROMIS Item Bank v2.0 Cognitive Function
- 7. Treatment Satisfaction Survey
- 8. Persistence of trends in patient-reported outcomes after stopping treatment will be evaluated at Visit 6 (Day 113).

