from this study is impractical and would delay and jeopardize completion of study enrollment. Multiple steps have been included in the trial design to account for the potential impact of pain from fibromyalgia on study results. To ensure that a significant component of the subjects daily pain NRS score is from inflammatory pain from joint/tendon involvements, subjects will be required to have arthritis and/or tendonitis on SELENA SLEDAI assessment or B score in the musculoskeletal domain of the BILAG 2004 assessment. The presence or absence of fibromyalgia and its severity will be assessed using the Fibromyalgia Symptom Score [107]. The absence versus presence of fibromyalgia (Fibromyalgia Symptom Score < 13 versus \geq 13 at Screening) will be used as a stratification variable at randomization and in subset analyses of the efficacy outcomes.

1.6.2 **Rationale for the Treatment Arm**

The JBT-101 doses selected for this study are within the range of doses that were well tolerated in previous Phase 1 and 2 studies and in a recently completed clinical trial in SSc, all sponsored by Corbus Pharmaceuticals Holdings, Inc. The JBT-101 oral doses selected for this study are 5 mg b.i.d., 20 mg q.d., and 20 mg b.i.d. Parallel dose assignment to JBT-101 in doses up to 20 mg b.i.d. is supported by a previous multiple ascending dose study and a Phase 2 study in humans in which JBT-101 doses up to 40 mg b.i.d. showed acceptable safety profiles and were well-tolerated. In a recently completed study of JBT-101 in systemic sclerosis and ongoing studies in dermatomyositis and cystic fibrosis (sponsored by Corbus) using similar doses to those proposed in this clinical trial (5 mg-40 mg daily), JBT-101 has been well tolerated with no severe AEs attributable to JBT-101. Each dose is expected have an acceptable safety profile, be well-tolerated, and provide clinical benefit, based on previous animal or human testing and the nature of the inflammatory components of SLE. Based on preclinical data and early higher dose clinical data, it is expected that any safety risk and clinical efficacy of JBT-101 in humans will be related to exposure. Based on extrapolation from animal models of inflammation, 5 mg q.d. was estimated to be about the median dose required for efficacy in humans. However, information from the cystic fibrosis study and from a cutaneous model of E. coli- induced inflammation [101] suggests that 5 mg b.i.d. may be more effective than the 5 mg q.d. dose:

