4.1 Inclusion Criteria

Individuals who meet ALL of the following criteria at Screening are eligible for enrollment:

- 1. Fulfill the updated ACR 1997 Revised Criteria for the Classification of Systemic Lupus Erythematosus [108]
- 2. ≥ 18 and ≤ 70 years of age at the time the Informed Consent Form is signed
- 3. At least 3 months treatment with an anti-malarial drug such as hydroxychloroquine or a history of intolerance, contraindication, or unwillingness to take an anti-malarial drug
- 4. Meets the SELENA SLEDAI definition of arthritis [109] or moderate arthritis or tendonitis that has not improved over the last month (i.e. BILAG B on the updated BILAG 2004 [110])

- 5. Seven-day average of maximum of daily pain NRS scores ≥ 4 out of 10 during screening with continued reporting of pain NRS scores on at least 67% of days between the Screening visit and randomization.
- 6. Overlap with polymyositis, systemic sclerosis, Sjögren's syndrome, or rheumatoid arthritis is allowed, if, in the site investigator's judgment, the predominant clinical features are those of SLE
- 7. Not expected by the site investigator to require a change in potential disease-modifying treatments for SLE from Screening through Visit 6 (Day 113)
- 8. Willing to not start or stop any NSAIDs or potential disease-modifying medications or supplements for SLE from Screening through Visit 6 (Day 113), unless a change is recommended by the site investigator or other treating physicians
- 9. Willing not to use any legal or illegal cannabinoids, including FDA-approved cannabinoids or cannabinoid-mimic drugs, or any illegal substance of abuse from Screening through Visit 6 (Day 113)
- 10. If a woman of child-bearing potential, willing to use one of the highly effective (failure rate < 1% per year) birth control method from Screening through Visit 6 (Day 113) or for 28 ± 3 days after the last dose of study product (See Appendix A: Reproductive Potential and Effective Methods of Contraception)
- 11. Willing to follow instructions, complete study procedures and attend study visits as required by this protocol

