6.1.5.1 SELENA SLEDAI (28 day assessment)

The SELENA SLEDAI is a validated measure of global disease activity in SLE and was modified from the original SLEDAI for the SELENA clinical trial in 1997. The original SLEDAI was developed in 1992; it includes both subjective reports from patients and objective findings from physicians and laboratory data [111]. The SELENA SLEDAI modification of the original SLEDAI changed some of the item definitions in order to clarify attribution and change in disease activity. These included changes to definitions of seizure activity, strokes, serositis, visual disturbances and proteinuria [109, 112].

The SELENA SLEDAI is a one page assessment that contains 24 items covering 9 organs systems and items are scored as either present or absent. Each item is assigned a weighted score. Two systems can score a maximum of 8 points each, 2 systems can score a maximum of 4 points each, 3 systems can score a maximum of 2 points each, and 2 systems can score a maximum of 1 point each. Scores range from 0–105 points. A score of 6 is considered clinically important and may affect the decision to treat. The original SLEDAI captured disease activity within the 10 days prior to assessment; however, this time period was extended to include the previous 30 days [113, 114].

The SLEDAI does not record improving or worsening, and does not include severity within an organ system. The sensitivity to change is less for the SLEDAI than other commonly used outcome measures in SLE [115].

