8 STATISTICAL CONSIDERATIONS AND ANALYTICAL PLAN

8.1 Sample Size and Power

A total of approximately 100 eligible subjects (approximately 25 per treatment arm) will participate in the study.

The primary hypothesis will be tested using the 3 degree of freedom (df) contrast comparing the difference in predicted means from Day 1 to Day 84 for each JBT-101 cohort versus placebo, where estimates will be derived from a random regression model (See Section 8.3.2.1, *Primary Efficacy Analysis*). The method of Stroup (1999) [123] was used to estimate power and sample size. To apply the method, we made reasonable assumptions about (1) the covariance matrix for the random effects and the residual variance, and (2) mean changes over time for each treatment group.

Subjects who complete the study will have approximately 84 NRS scores assessed daily. To derive the within-subject covariance matrix, we need the within-subject correlation matrix and the standard deviation. We assume the daily assessments have an AR(1) within-subject correlation structure, which seems reasonable based on preliminary data on 24 subjects assessed on days 1, 14, and 28 [101]. Based on this preliminary data, the correlation coefficient for assessments 1 day apart is very high (estimated as 0.9775). The standard deviation (SD) of the NRS is assumed to be the same for each day and likely to be on the range from 1.3 to 1.6. The range is based on a study by Farrar (2001) [124] that examined data from 10 clinical trials including 2724 patients with a variety of conditions characterized by chronic pain who had baseline pain of \geq 4 on the NRS. The study suggests that patient's perceptions of pain and improvement is similar and consistent across disease indications. Results of this study influenced the recommendations on clinical importance of treatment effects on pain in clinical trials (IMMPACT) group [125].

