8.2 Analysis Populations

8.2.1 Modified Intent-to-Treat Population

The modified Intent-to-Treat population (mITT) will consist of all randomized subjects who have received at least one dose of study product. The mITT population will be used for all efficacy analyses and will include subjects under the treatment to which they were randomized, regardless of compliance with assigned treatment.

8.2.2 **Per Protocol Population**

The per protocol population (PP) will consist of mITT subjects who:

- complete Visit 3 (Day 29), without missing more than 7 days of study product between Visit 1 (Day 1) through Visit 3 (Day 29).
- have ≥ 80% compliance with study drug administration from Visits 1- 5 (Days 1-85), as assessed by numbers of capsules of study product returned to the site, excluding periods off study drug when directed per protocol by the site investigator or treating physician)
- complete the study without protocol violations deemed likely to effect the efficacy outcomes of interest

A masked data review panel will evaluate deviations from the protocol including, for example, violations of entry criteria, departures from assigned treatment regimen, modifications of concurrent therapy, failure to complete study visits, or administration of study procedures outside the specified visit windows to determine if occurrence of these deviations should exclude subjects from the PP population.

The PP population will be used for secondary efficacy.

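### The SLE Responder Index needs a 4-point SELENA SLEDAI fall, but no SLEDAI floor is set at entry or in the analysis set, so subjects starting at 0 to 3 cannot respond

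*Protocol*

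**What the plan says.** **Responder definition.** Protocol 3.2.2 (and the synopsis) requires three things together: a "point reduction in SELENA-SLEDAI score" of at least 4, a limit on new BILAG A or B scores, and no worsening of the Physician's Global Assessment.

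**The scale.** Section 6.1.5.1 states that "Scores range from 0–105 points" and that "items are scored as either present or absent".

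**Entry.** Inclusion criterion 4 in Section 4.1 reads "Meets the SELENA SLEDAI definition of arthritis [109] or moderate arthritis or tendonitis that has not improved over the last month", the second route being a BILAG B. Section 1.6.1 repeats the alternative: "subjects will be required to have arthritis and/or tendonitis on SELENA SLEDAI assessment or B score in the musculoskeletal domain". Sections 4.1 and 4.2 set no minimum SELENA SLEDAI total. Eligibility is judged at Screening, up to 42 days before Visit 1 (Section 6.4.1).

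**Related endpoint.** Section 3.2.2 also lists "Presence or absence of arthritis on the SELENA SLEDAI". Section 8.3.2.2 analyses it in the same manner as the categorical pain outcomes, by contingency tables against treatment group.

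**Analysis set.** Section 8.2.1: "The mITT population will be used for all efficacy analyses". Neither that definition nor the per-protocol definition in 8.2.2 depends on baseline SLEDAI or baseline arthritis.

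**The concern.** An endpoint defined by a minimum fall needs subjects who have that far to fall. Entry here rests on musculoskeletal activity and pain, not on a SLEDAI total. Two kinds of subject can therefore reach Visit 1 with a score below 4:

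- a subject admitted for BILAG B tendonitis with no SLEDAI arthritis and little activity elsewhere;
- a subject admitted through either route who improved between Screening and Visit 1.

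Neither can meet the responder definition. The arthritis endpoint has a related limit: someone without SLEDAI arthritis at Visit 1 has nothing to resolve.

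Section 8.3 says the secondary analyses should help to design, choose doses for and power later pivotal studies. A responder rate held down by an unreported number of subjects who could not respond is a poor input for that. Randomisation is stratified on pain score and Fibromyalgia Symptom Scale only (Section 3.1.1), so the number of such subjects per arm is left to chance.

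**Working it through.** The protocol states no power, sample size or expected rate for the Responder Index, so there is no figure of its own to reproduce. The check is one logical step and some illustrative arithmetic.

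**Step 1: who can respond.** The minimum score is 0, so the largest possible fall equals the Visit 1 score.

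| Visit 1 SLEDAI | Largest fall | Fall of at least 4 possible? |
|---|---|---|
| 0, 1, 2, 3 | 0, 1, 2, 3 | No |
| 4 or more | 4 or more | Yes |

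**Step 2: dilution.** Let f be the share of each arm below 4 at Visit 1 (not in the protocol; 10% to 40% assumed). The observed responder rate is (1 − f) × the rate among subjects able to respond. The ceiling is therefore 1 − f, and the observed difference is (1 − f) × the true difference. For a true difference of 20 points:

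- f = 10%: 0.9 × 20 = 18 points
- f = 20%: 0.8 × 20 = 16 points
- f = 40%: 0.6 × 20 = 12 points

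**Step 3: chance imbalance.** With 25 per arm (Section 8.1), the SD of the between-arm difference in f is √(2f(1 − f)/25), which is 8.5, 11.3 and 13.9 points at f = 10%, 20% and 40%. That is not the shift in the endpoint. The responder rate moves by the imbalance times the response rate among subjects able to respond. With assumed rates of 30% to 60%, one SD of imbalance moves it by:

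- f = 10%: 8.5 × 0.3 to 8.5 × 0.6, about 2.5 to 5.1 points
- f = 20%: 11.3 × 0.3 to 11.3 × 0.6, about 3.4 to 6.8 points
- f = 40%: 13.9 × 0.3 to 13.9 × 0.6, about 4.2 to 8.3 points

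**Step 4: what restriction buys.** Assume 30% v 60% among subjects able to respond, two-sided alpha 0.05 and a pairwise comparison of proportions (normal approximation). The whole-mITT analysis has 25 per arm and rates multiplied by (1 − f). The restricted analysis has 25 × (1 − f) per arm and undiluted rates.

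| f | Whole mITT: difference | Whole mITT: power | Restricted: n per arm | Restricted: difference | Restricted: power |
|---|---|---|---|---|---|
| 0 | 30 points | 57% | 25 | 30 points | 57% |
| 10% | 27 points | 49% | 22.5 | 30 points | 53% |
| 20% | 24 points | 42% | 20 | 30 points | 48% |
| 40% | 18 points | 30% | 15 | 30 points | 37% |

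Restriction recovers the full difference but only part of the lost power.

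**Step 5: the arthritis endpoint.** A subject scored absent at Visit 1 cannot move to absent, but items are scored afresh at each assessment, so the subject can move to present. Only improvement is closed off.

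**The case against.** **These endpoints carry little weight in the plan.** Section 1.6 does not expect secondary changes to reach significance, Section 8.3 calls these analyses exploratory, and Section 8.8 treats their p-values as descriptive. No power is claimed for the Responder Index, and the step 4 figures stay low under either analysis. All of this stands and limits the importance of the point.

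**Other endpoints cover these subjects.** Section 3.2.2 also lists the SELENA SLEDAI score, BILAG 2004 including its musculoskeletal domain, joint counts and the Physician's Global Assessment. A tendonitis entrant is followed on the instrument that admitted them. This is true, but it does not make the Responder Index rate easier to interpret.

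**Denominators belong in the SAP.** Often they do, and an SAP not seen here may set evaluable subsets. However, Section 8.2.1 already fixes mITT for all efficacy analyses. Section 8.3.2.2 allows added covariates, but these cannot make an impossible response possible.

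**Stronger readings that the documents do not support.** A reader might infer any of the following:

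- *Subjects without SLEDAI arthritis at Visit 1 count as a good outcome throughout.* They can develop arthritis and be scored present, and the protocol does not define absence as success.
- *The comparison is biased.* Randomisation spreads low-scoring subjects across arms apart from chance.
- *Every BILAG B entrant is affected.* One with 4 or more points from other organ systems can respond.
- *Only the BILAG route is open to this.* Screening may precede Visit 1 by up to 42 days, so a SLEDAI-arthritis entrant may also start low.

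**Conclusion.** The point holds for the Responder Index as a matter of arithmetic: Visit 1 SLEDAI of 0 to 3 rules out response, nothing in Section 4 prevents such entry, and Section 8.2.1 keeps these subjects in the denominator. The ceiling is 1 − f and the difference shrinks by (1 − f). How much this matters depends wholly on f, which the protocol does not give; the 10% to 40% range and the 30% v 60% rates are assumptions. The result is dilution and added noise on an exploratory secondary endpoint.

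For SLEDAI arthritis, the supported statement is narrower: subjects without it at Visit 1 cannot improve, although they can worsen. The change is worth making because it gives a clearer quantity at almost no cost, not because it rescues power.

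**What to change.** In Sections 3.2.2 and 8.3.2.2, with Section 8.2.1 adjusted to match:

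1. Analyse the SLE Responder Index in mITT subjects with a Visit 1 SELENA SLEDAI of at least 4. Report the number excluded per arm, and give the whole-mITT result as supportive.
2. For SLEDAI arthritis, report resolution among subjects with arthritis at Visit 1 and new onset among those without it. Keep the whole-mITT presence/absence analysis, so that worsening stays visible.

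Both subsets are defined by pre-dose data already collected at Visit 1, so the comparisons within them remain randomised. The cost is wording, a little extra tabulation, and smaller denominators for these two endpoints. Eligibility, visits and data collection do not change.
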